**Table 1-1. Schedule of Activities**

	SCR a	Treatment Period (21-day Cycles) b								EoT d	STFU e	LTFU f	Notes	
		D1	D3	D5	D8	D10	D12	D15 c	D16-21					
B-cells and immunophenotype	X	X					(X)			X	X		(X): Day 12 of Cycle 1 only	
Complement	X	X								X			Should be assessed before the start of infusion and 3 hours after the start of infusion ( $\pm$ 10 min), or if a subject experiences a Grade $\geq$ 2 IRR/CLS/CRS or other hypersensitivity reaction. See Section 10.2.2.3 for details.	
Histamine	X	X								X				
Cytokines	X	X								X				
Immunoglobulins	X	X								X			Should be assessed before the start of infusion and 3 hours after the start of infusion ( $\pm$ 10 min).	
Optional tumor tissue biopsy										X			Applicable to subjects who had consented for this procedure, exhibit PD, and have accessible peripheral lymph node(s).	
Efficacy Assessments														
Radiological assessment	X	Every 6 weeks ( $\pm$ 1 week) starting from C1D1, until disease progression, death, or lost to follow-up AND For subjects without response or SD at EoT: within 7 days of the EoT Visit ( only if the previous tumor scan has been performed $>$ 4 weeks before the EoT Visit)								The investigator is encouraged to obtain the screening tumor scan as close as possible to the start of treatment. The original schedule needs to be maintained even if there is a delay in dosing. Subjects who continue to receive treatment beyond progression should also have repeat scans.				
EQ-5D	X	(X)								X	X		(X): Collected D1 of every even cycle (C2, C4, C6, etc)	
Study Treatment														
Premedication		X	X	X	X	X	X	(X)					Administered within 60 minutes prior to MT-3724 infusion. Refer to Section 6.1.2 for guidance. (X): Only when weekly dosing is implemented.	
MT-3724 infusion (TIW)		X	X	X	X	X	X						The first 3 doses of Cycle 1 must be administered at least 2 days (approx. 48 hours) apart. All subsequent doses must be given within $\pm$ 1 day of scheduled visit. All 6 doses must be given within the first 16 days, the doses should be at least 20 hours apart, and should not be administered on more than 2 consecutive days.	
MT-3724 infusion (weekly schedule) h		X			X			X					Starting with Cycle 3, doses will be administered weekly. Doses must be given within $\pm$ 2 day of scheduled visit.	

ABC = activated B-cell; ADA = anti-drug antibodies; AE = adverse event; BMI = body-mass index; BP = blood pressure; C = cycle; CAR-T = chimeric antigen receptor T-cell therapy; CLS = capillary leak syndrome; CK = creatine phosphokinase; CRS = cytokine release syndrome; CT = computerized tomography; D = day; ECG = electrocardiogram; ECHO = echocardiogram; ECOG = Eastern Cooperative Oncology Group; eCrCl = estimated creatinine clearance; eCRF = electronic case report form; EOI = end of infusion; EoT = end of treatment; EQ-5D = EuroQol Group Quality of Life – 5-dimensions; GCB = germinal center B cell; HbA1c = glycated hemoglobin; HBV = hepatitis B virus; HCV = hepatitis C virus; HIV = human immunodeficiency syndrome; LTFU = long-term follow-up; NHL = non-Hodgkin's lymphoma; HR = heart rate; IRR = infusion-related reaction; LVEF = left ventricular ejection fraction; MRI = magnetic resonance imaging; MUGA = multigated acquisition; NAb = neutralizing antibody; NYHA = New York Heart Association; OTC = over-the-counter; PD = progressive disease; PK = pharmacokinetic; RNA = ribonucleic acid; RR = respiratory rate; SCR = screening; SCT = stem cell transplant; SD = stable disease; STFU = short-term follow-up; TIW = three times a week.

- a The screening period is up to 35 days prior to enrollment. All local/central laboratory safety assessments and radiological assessments must be collected within 28 days prior to enrollment.
- b All assessments are performed any time before dosing unless otherwise indicated. Predose assessments may be performed up to 1 day prior to dosing (except for cytokines/immunoglobulins/complement/histamine which should be collected just prior to dosing).
- c The Day 15 visit is applicable for subjects receiving the weekly dosing schedule.
- d Upon discontinuation of treatment, as soon as possible (up to 14 days) after the last dose, and before the start of new therapy.
- e A STFU visit occurs 30 days ( $\pm$  3 days) after the last dose. The STFU visit can be done via a clinic visit (recommended) or via a telephone call (if subject cannot attend a clinic visit or has started a new anticancer treatment or a new NHL treatment). If performed via a telephone call, only AEs and concomitant medications will be collected.
- f LTFU visits should occur every 3 months ( $\pm$  14 days) after the last dose of MT-3724 for up to 18 months from the last dose. The LTFU Visits will be performed via a telephone call to collect the information about the NHL status (relapsed or not), the start of any new therapy for NHL since the last study visit/phone call or death. Subjects with SD or response should also be followed for radiology assessment until progressive disease, start of new anticancer treatment, or death.
- g When PK, ECG, and vital signs assessments are scheduled to occur at the same time point, the ECG and vital signs should be done first and in that order, with the timing of assessments based on collecting the PK sample at the protocolled time (eg, if the PK sample is expected 2 hours after EOI, collect the PK sample 2 hour after the infusion, and ECG/VS within 10 minutes before the PK sampling).
- h The weekly dosing schedule follows procedures on Days 1, 8 and 15.

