#### **4.1.3      Parts 3 and 4**

All study procedures will be the same for Parts 3 and 4. After eligibility is assessed in the screening period (up to 35 days), subjects enter the treatment period. Each treatment cycle will be 21 days in length. Treatment will continue until death, disease progression, unacceptable toxicity, withdrawal of consent, or another reason for withdrawal, or until study discontinuation. Refer to [Section 6.1.1.4](#) for details regarding treatment beyond progression.

**End of Treatment:** After discontinuation from treatment, all subjects should undergo the End of Treatment (EoT) Visit as soon as possible (up to 14 days) after the last dose of MT-3724 and before start of new therapy.

**Short-term Safety Follow-up:** The Short-term Follow-up (STFU) Visit for safety assessment should occur 30 days ( $\pm$  3 days) after the last dose of MT-3724, except for subjects who withdrew consent and objected to further data collection, started new therapy for DLBCL or started another investigational drug.

**Long-Term Follow-up:** Long-term Follow-up (LTFU) Visits should occur every 3 months ( $\pm$  14 days) after the last dose of MT-3724 for up to 18 months from the last dose. Subjects who discontinue the study for disease progression will be followed only for OS. Subjects with CR, PR, or SD should also be followed for radiology assessment until progressive disease (PD), death, or start of new anticancer treatment.

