### **8.1.1 Screening and Enrollment**

A signed written ICF will be obtained before any screening procedure may begin.

Screening procedures will be performed within 35 days before the start of treatment on C1D1, except for central and local laboratory safety assessments and radiographic assessments (must be collected within 28 days of start of treatment) and the determination of LVEF (see [Section 8.4.7](#) for the permitted windows for this assessment).

After the investigator determines that all eligibility criteria have been fulfilled (see [Section 5](#)), the medical monitor should review the screening results and acknowledge the investigator's decision that the subject may start treatment.

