#### 9.3.1.1 Baseline Definition

The assessment obtained (and entered into EDC) at the most recent time before the start of MT-3724 treatment will be the baseline for all post-baseline assessments.

For all efficacy endpoints, the tumor scan obtained before MT-3724 Dose 1 during the screening (if available) will serve as the baseline; Pre-study tumor scan should be collected as close as possible to the start of treatment and evaluable for the ICR (ie, performed according to the Imaging Acquisition Guidance provided in the Imaging Manual).

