### **9.3.2.3        Quality of Life**

Quality of life is assessed via the EQ-5D. The EQ-5D consists of the EQ-5D descriptive system and the EQ visual analogue scale. The EQ-5D descriptive system includes 5 dimensions: mobility, self-care, usual activities, pain/discomfort and anxiety/depression. The response for each of the dimensions is ordered categorical: 1 = no problems, 2 = slight problems, 3 = moderate problems, 4 = severe problems and 5 = unable to/extreme problems. The EQ-5D domains will be summarized descriptively in terms of the percent of subjects falling into each ordered category at any given timepoint; the data will also be explored by cumulative and adjacent logit analyses.

The EQ visual analogue scale records the respondent’s self-rated health on a vertical, visual analogue scale where the extremes are ‘100 = Best imaginable health state’ and ‘0 = Worst imaginable health state’. The change in visual analog scale score from baseline to any given time point will be summarized descriptively.

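### No EQ-5D is taken on Cycle 1 Day 1, so the EQ VAS baseline is the screening form, up to 35 days before first dose, and any change before MT-3724 enters the change from baseline

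*Protocol*

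**What the plan says.** - **Schedule.** In Protocol Table 1-1 the EQ-5D row is marked at screening, end of treatment (EoT) and short-term follow-up (STFU). The Day 1 mark is in brackets, and the note on it reads "X): Collected D1 of every even cycle (C2, C4, C6, etc".
- **Screening window.** Protocol 8.1.1: "Screening procedures will be performed within 35 days before the start of treatment on C1D1". The exceptions there are laboratory safety tests, radiology and LVEF. Footnote a of Table 1-1 applies the tighter limit in the same way: "All local/central laboratory safety assessments and radiological assessments must be collected within 28 days prior to enrollment". EQ-5D is in neither group, so it keeps the full 35 days.
- **Baseline.** Protocol 9.3.1.1 takes the assessment obtained "at the most recent time before the start of MT-3724 treatment will be the baseline".
- **Analysis.** Protocol 9.3.2.3: "The change in visual analog scale score from baseline to any given time point will be summarized descriptively". The five domains are summarized as percentages of subjects per response category at each time point, with exploratory cumulative and adjacent logit analyses.
- **SAP.** It is based on protocol v7.0 (Parts 1 and 2) and contains no EQ-5D analysis, so it neither adds to nor changes the above.

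**The concern.** A change score is only as good as its starting point. With no form on C1D1, the starting point for EQ VAS is whatever was recorded at screening, and the weeks between that form and the first infusion are counted in the change from baseline alongside the weeks on drug. These subjects have relapsed or refractory DLBCL after at least two regimens, so their health need not be stable over that time. There is no concurrent control arm whose change over the same period could be subtracted.

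Other repeated measures do not have this gap. Table 1-1 repeats weight, ECOG, vital signs, hematology, chemistry, anti-drug antibodies and B cells on Day 1 of each cycle, including C1D1 before dosing. Thyroid function follows an alternate-cycle rule too, but on odd cycles, which does include C1D1.

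At stake is how the EQ VAS summary can be read. No analysis can later recover a predose value that was never collected.

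**Working it through.** The plan gives no figure of its own on this point, so the check is on timing.

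**Inputs**
- Screening lead L (days from the EQ-5D form to C1D1): 0 to 35, from Protocol 8.1.1. Footnote a of Table 1-1 counts its 35 days to enrollment; the figure used here is the one that 8.1.1 counts to C1D1.
- Cycle length: 21 days (Protocol 4.1.3, "Each treatment cycle will be 21 days in length"). C2D1, C4D1 and C6D1 are therefore nominally 21, 63 and 105 days after C1D1.
- Delay between cycles: up to 14 days before the medical monitor must be consulted (Protocol 6.1.1.3). As an upper range, C2D1 is taken as 21 + 14 = 35 days after C1D1.
- Predose window: up to 1 day before dosing (Table 1-1, footnote b).

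**Step 1. Which form is the baseline?** EQ-5D is due at screening and then on Day 1 of even cycles. Cycle 1 is odd. The only scheduled form before first dose is the screening form, so 9.3.1.1 selects it.

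**Step 2. What the change score contains.** For a visit v,

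VAS(v) − VAS(screening) = [VAS(v) − VAS(C1D1)] + [VAS(C1D1) − VAS(screening)].

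The second bracket is change before MT-3724. It is not observed under the current schedule, and for a given subject it is the same amount in every later change score.

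**Step 3. Share of the interval that precedes MT-3724.** Share = L / (L + T), where T is the number of days from C1D1 to the visit.

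| Lead L | C2D1, no delay (T = 21) | C2D1, 14-day delay (T = 35) |
|---|---|---|
| 7 days | 7/28 = 25% | 7/42 = 16.7% |
| 14 days | 14/35 = 40% | 14/49 = 28.6% |
| 28 days | 28/49 = 57.1% | 28/63 = 44.4% |
| 35 days (maximum) | 35/56 = 62.5% | 35/70 = 50% |

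At later visits with the 35-day maximum lead and no delay: C4D1, 35/(35 + 63) = 35.7%; C6D1, 35/(35 + 105) = 25%.

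These are shares of time, not of VAS change. By Step 2, the falling share at later visits does not mean that the predose amount shrinks.

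**Step 4. With a predose form on C1D1.** L becomes 0 to 1 day, and the share at C2D1 is at most 1/22 = 4.5%.

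**The case against.** The schedule reading is not in dispute. The case on the other side is about how much may be built on it, and most of it stands.

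- **Direction.** A reader might infer that decline during screening is being counted as harm from MT-3724. The documents hold no EQ-5D data for that period. Decline is plausible in this disease, but exclusion 7 requires most toxicity from prior anticancer therapy to be Grade 1 or lower before treatment starts, so some subjects may be recovering. Only a change of unknown sign is supported.
- **Untreated time.** A reader might call the 35 days untreated. Exclusion 2 bars other DLBCL treatment for 4 weeks, or for small molecules 5 half-lives or at least 2 weeks, and palliative radiation to non-target lesions may be allowed. The days are before MT-3724; they need not be free of all therapy.
- **Domains.** It is tempting to extend the point to domain comparisons with baseline. Section 9.3.2.3 plans none; only the VAS has a planned change from baseline.
- **Size in VAS points.** A monthly rate of change could be assumed and multiplied out, but the documents supply no such rate.
- **Consistency.** Radiology, the other entry under efficacy assessments in Table 1-1, also uses a screening baseline, up to 28 days old. So a screening baseline is not out of line with the protocol. However, sites are encouraged to scan as close to treatment start as possible, and EQ-5D has no such instruction.
- **Importance.** EQ-5D is not among the visible primary, key secondary or secondary endpoints; the exploratory rows are blank in the public text, so its intended role cannot be judged. Even with a C1D1 baseline, a single-arm change cannot be credited to the drug, because the natural course after C1D1 remains.

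None of this supplies a predose value on C1D1 or limits the age of the baseline.

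**Conclusion.** The point holds as a minor weakness of design, not as an error or a contradiction. As scheduled, the EQ VAS baseline is the screening value, up to 35 days before first dose, and whatever happens to health in that time, in either direction, is part of every EQ VAS change from baseline. At C2D1 without delay, the period before MT-3724 makes up 25% to 57% of the interval for leads of 7 to 28 days, and 62.5% at most. At the maximum lead the share is 36% at C4D1 and 25% at C6D1.

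This rests on nominal cycle timing and on the permitted window; actual screening leads are not given, and 35 days is a ceiling rather than an expected value. A subject who stops in Cycle 1 has EoT rather than C2D1 as the next form, which alters the interval but not the baseline. The effect stays within a descriptive quality-of-life summary. The Part 4 primary test of overall response rate does not use EQ-5D and is untouched.

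**What to change.** - **Table 1-1:** collect EQ-5D on C1D1, before premedication and dosing, as well as on Day 1 of even cycles. The form can be added to the screening one or moved from it.
- **Section 9.3.2.3:** state that the predose C1D1 value is the EQ-5D baseline, and that the screening value, if still collected, is used only when the C1D1 value is missing.

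The cost is one short questionnaire at a visit that already has predose assessments, or no extra form if the screening one is moved, plus one line in the table and one sentence in the analysis section. If the form is moved, there is no fallback for a subject whose C1D1 form is missed; keeping both avoids that and also makes the change before first dose visible.

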## 5 STUDY POPULATION

**NOTE:** The investigator or sub-investigator must judge all pre-admission vital signs, physical examination (PE), laboratory or any safety variables to be within normal limits or clinically insignificant. If local standard of care (SoC) procedures or tests were performed prior to signing of the informed consent form (ICF) but are still within 35 days (or 28 days for laboratory safety and radiographic assessments) of the planned dose Day 1, then those results/data can be used for the intended protocol screening procedure. If various parameters within a given procedure are missing from the SoC procedures, then only those missing parameters need to be collected. The medical monitor will also review all screening data to confirm each subject's eligibility prior to dosing initiation. Any laboratory results that exclude study participation may be repeated to confirm accurate exclusion from the study. A subject who is no longer excluded upon retest will be reviewed again by the medical monitor prior to dosing initiation.

In addition, prior to first dose of MT-3724 on Cycle 1 Day 1 (C1D1), the investigator must confirm there have been no changes in the subject's health that would render them medically inappropriate to begin protocol therapy.

Before any study-specific activities/procedures, the appropriate written informed consent must be obtained (see [Section 10.1.4](#)). Prospective approval of protocol deviations to recruitment and enrollment criteria, also known as protocol waivers or exemptions, is not permitted.

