### Prior or Current Therapies

1. Received any amount of anti-CD20 mAbs within the following periods before the start of treatment:
  - a. Rituximab (Rituxan®/MabThera® or rituximab biosimilar): within 84 days (12 weeks); if a subject has received rituximab within 37 weeks before the start of treatment, then serum rituximab level must be negative ( $< 500$  ng/mL) at screening.
  - b. Obinutuzumab (Gazyva®/Gazyvaro®): 184 days
  - c. Ofatumumab (Arzerra®): 88 days
  - d. Any other anti-CD20 agents (eg, investigational agents), the washout period is 5 half-lives. The investigator must contact the medical monitor to discuss the most

appropriate washout for non-approved CD20-targeting agents, where the half-life ( $t_{1/2}$ ) is not known.

2. Received approved or investigational treatment for DLBCL (except anti-CD20 agents where exclusion criterion 1 applies and radioimmunoconjugates) within 4 weeks before the start of treatment. For small molecules (MW < 0.9 kDa), the washout is 5 half-lives or at least 2 weeks. Radioimmunoconjugates are excluded within 12 weeks before the start of treatment.
3. Received radiation therapy to tumor lesions that would serve as target lesions (measurable disease) within 4 weeks before the start of treatment, unless the lesion exhibited objective progression between radiation therapy and screening according to the Lugano Classification ([Cheson, 2014](#)).
  - a. Palliative radiation therapy to non-target lesions may be permitted at the investigator's discretion after consultation with the medical monitor and sponsor. See [Section 6.5](#) for more information on permissible use of palliative radiotherapy.
4. Require the use of systemic immune modulators during study treatment:
  - a. Systemic immune modulators include, but are not limited to, systemic corticosteroids at doses > 20 mg/day of prednisone equivalent, cyclosporine and tacrolimus. Please see [Section 6.1.3](#) for more details and exceptions.
  - b. The use of non-steroidal anti-inflammatory drugs (NSAIDS) is permitted.
5. Received any live vaccines within 4 weeks before the start of treatment.
6. Prior treatment with MT-3724.

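### The baseline tumour scan can predate the last dose of a prior small-molecule lymphoma drug by up to 14 days, so shrinkage from that drug can count toward an MT-3724 response (mainly PR)

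*Protocol*

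**What the plan says.** Four protocol rules bear on this point.

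- **Age of the scan.** Table 1-1, footnote a: "All local/central laboratory safety assessments and radiological assessments must be collected within 28 days prior to enrollment". Section 8.1.1 uses a different anchor: "radiographic assessments (must be collected within 28 days of start of treatment".
- **Reuse of earlier scans.** The note in Section 5 accepts standard-of-care procedures done before consent in place of the screening procedure, on condition that they "are still within 35 days (or 28 days for laboratory safety and radiographic assessments) of the planned dose Day 1".
- **Washout.** Section 5.2, exclusion 2, sets 4 weeks before treatment for most DLBCL therapy. It then adds: "For small molecules (MW < 0.9 kDa), the washout is 5 half-lives or at least 2 weeks". Anti-CD20 agents and radioimmunoconjugates have their own, longer periods.
- **Use of the scan.** Section 9.3.1.1 makes the screening scan the baseline for all efficacy endpoints and attaches no condition about when prior therapy ended.

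On timing relative to treatment, Table 1-1 goes no further than this: "The investigator is encouraged to obtain the screening tumor scan as close as possible to the start of treatment". Section 9.3.1.1 has similar advice. The SAP supplied is based on protocol v7.0 (Parts 1 and 2) and adds no rule for Part 4.

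**The concern.** The scan window and the washout are set independently. A subject can be scanned on Day -28, take the previous small-molecule drug until Day -14, start MT-3724 on Day 1, and comply with every stated rule. Any tumour shrinkage caused by the earlier drug between Day -28 and C1D1 then lies on the MT-3724 side of baseline.

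Part 4 has a single arm and its primary endpoint is ORR, so there is no comparator in which the same carry-over would appear. Blinded central review does not help, because the readers use the same baseline scan. Entry requires relapsed or refractory disease after at least two regimens, but not progression on the most recent agent, so residual activity of that agent is possible. The protocol guards against the same problem for radiotherapy: exclusion 3 bars recent radiation to a target lesion unless that lesion has since progressed. Systemic drugs have no counterpart.

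The category most exposed is PR. In Table 10-5, CT-based PR is a fall of at least 50% in SPD, and PET-based PR needs reduced uptake; both are judged against baseline. CR is essentially an absolute criterion (5-point score of 1 to 3, or nodes of at most 1.5 cm with no extralymphatic disease).

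**Working it through.** **Inputs**
- Oldest permitted scan: 28 days before C1D1 (Sections 5 and 8.1.1) or 28 days before enrollment (Table 1-1, footnote a).
- Latest permitted prior dose: 14 days before treatment for small molecules, 28 days for other DLBCL drugs under exclusion 2.
- Part 4 rule: success if at least 23 of 88 respond; null 17%, alternative 32%, one-sided alpha below 0.025, stated power 90.4% (Sections 4.1.2 and 9.1).

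**The plan's own figure.** With X binomial on 88 subjects, P(X ≥ 23 | 0.17) = 0.0201 and P(X ≥ 23 | 0.32) = 0.9039. The stated 90.4% reproduces. A boundary of 22 would give alpha 0.0364, so 23 is the smallest valid boundary. The sample size is not in question.

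**Overlap = scan window minus washout**

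| Prior drug | Window counted from C1D1 | Window counted from enrollment, k days before C1D1 |
|---|---|---|
| Small molecule, 2 weeks | 28 - 14 = 14 days | 14 + k days |
| Other, 4 weeks | 28 - 28 = 0 days | k days |

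The documents do not give k. The 14 days takes 2 weeks as the minimum washout. If the wording were read as allowing 5 half-lives when that is shorter, assumed half-lives of 6 to 48 hours give 1.25 to 10 days of washout and an overlap of 26.75 to 18 days. I do not rely on that reading.

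**Illustration at a true ORR of 17%.** The documents give no frequency, so these inputs are assumptions.

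(a) Suppose m of the 88 count as responders through carry-over and the rest respond at 17%. The false-positive rate is P(X ≥ 23 - m | n = 88 - m, 0.17):

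| m | Rate |
|---|---|
| 0 | 0.0201 |
| 1 | 0.0323 |
| 2 | 0.0504 |
| 3 | 0.0765 |

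(b) Suppose a share f of subjects is exposed and a share q of their would-be non-responders is converted. The apparent rate is 0.17 + 0.83 × f × q.
- f = 5%, q = 10%: 0.17 + 0.83 × 0.005 = 0.1742; false-positive rate 0.026. Expected converted subjects: 88 × 0.83 × 0.005 = 0.37.
- f = 10%, q = 20%: 0.17 + 0.83 × 0.02 = 0.1866; false-positive rate 0.052. Expected converted subjects: 88 × 0.83 × 0.02 = 1.46.

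(c) The false-positive rate passes 0.025 once the apparent null rate reaches about 17.35%, that is, 0.35 percentage points above 17%.

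**The case against.** **Systemic lymphoma treatment is prohibited during the study.** Section 6.1.3 says so, and Section 8.1 counts screening as the first study period. On that reading no prior drug could follow a scan taken after consent, and only reused pre-consent scans would leave a gap. This narrows the point but does not clearly close it. Exclusion 2 counts washout from the start of treatment, not from consent. The list in 6.1.3 also states a pre-treatment period explicitly for live vaccines, which suggests that its other entries do not automatically reach back into screening. A reused pre-consent scan is untouched on either reading.

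**Carry-over would have to last.** The first scheduled scan is 6 weeks ± 1 week after C1D1, so at least 5 + 2 = 7 weeks after a drug stopped on Day -14. Confirmation should follow 4 to 8 weeks later, so at least 11 weeks after stopping. This makes carry-over responses less likely. It does not exclude them, since both scans are compared with the same baseline.

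**Direction.** Many of these subjects will have had drugs that were failing, and growth between an early scan and C1D1 biases against MT-3724. A reader might infer that ORR is inflated overall; the documents do not support that. The net direction is unknown.

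**Scope.** A reader might extend the point to all prior lymphoma therapy. With both windows counted from C1D1, dosing after the scan is possible only for small molecules. A reader might also add palliative radiotherapy to non-target lesions. That case is weak: CT-based PR depends on target-lesion SPD, and CT-based CR also needs the target nodes to regress, so the likely effect is PR versus CR with ORR unchanged.

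**Existing controls.** The medical monitor reviews screening data before dosing, and start and stop dates of each prior agent are recorded (Section 8.2.3). Affected subjects can therefore be identified, but no analysis is planned that uses those dates. The Imaging Manual, which may say more, is not among the documents.

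**Conclusion.** The gap is real but narrow. The stated rules permit up to 14 days of a previous small-molecule drug after the baseline scan, and resulting shrinkage can be counted toward an MT-3724 response, mainly PR. For drugs with a 4-week washout the overlap is 0 days unless footnote a's enrollment anchor is used. That anchor conflicts with Sections 5 and 8.1.1 and needs reconciling in any case.

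The overlap is permitted, not certain, and its frequency is unknown. The false-positive figures show only how little slack the 23-of-88 rule has: one carry-over responder takes 0.020 to 0.032, two to 0.050, and 5% exposed with 10% of their non-responders converted gives 0.026. They model inflation alone and are not estimates. A reader might be tempted to apply a 2% or 4% conversion to every non-responder (0.052 and 0.113). Only subjects whose last drug was a small molecule taken after the scan are exposed, so those rates should not be read as expected error. The design figures (n = 88, boundary 23, power 90.4%) stand.

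**What to change.** 1. In Table 1-1 footnote a, Section 8.3.1 and Section 9.3.1.1, require the baseline scan, including any reused standard-of-care scan, to be obtained after the last dose of prior systemic anti-lymphoma therapy and within 28 days before C1D1. This replaces the enrollment anchor and agrees with Sections 5 and 8.1.1.
2. Leave the washout periods as they are. The required order reduces the permitted overlap to 0 days without touching them.
3. Add a sensitivity analysis of Part 4 ORR that counts as a non-responder any subject whose baseline scan predates the last prior dose, using the stop dates already collected.

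**Cost.** One sentence in three places and one extra table. A minority of subjects could not reuse an older standard-of-care scan and would need the screening scan taken after stopping prior therapy, which fits within a 2-week washout. Sample size, boundary, alpha and power do not change.
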